**Table 5: Attributes of Primary and Key Secondary Estimand**

Estimand Attribute	Subjects no longer meeting diagnostic criteria of post-COVID POTS as measured by standardized standing test.
Population	Adults ( $\geq 18$ years of age) with post-COVID-19 Postural Orthostatic Tachycardia Syndrome (POTS)
Treatment	Randomized IMP (blinded IgPro20 or blinded placebo)

Endpoint	
Primary: Proportion of subjects no longer meeting diagnostic criteria of post-COVID POTS as measured by standardized standing test.
 
Key secondary:
 
 
Change from baseline in orthostatic intolerance score (OI) of COMPASS-31 at the end of the Double-blind Treatment Period. Change from baseline in COMPASS-31 total score (TS) at the end of the Double-blind Treatment Period.
 
Change from baseline in HR increase within 10 minutes of standing test at the end of the Double-blind Treatment Period.
 
		
Intercurrent Event	Strategy	Description	Imputation details
Treatment (IMP) discontinuation due to LoE, related adverse event or lack of compliance	Composite / Hypothetical	Discontinuation due to lack of efficacy will be treated as a failure. Only data collected prior to treatment (IMP) discontinuation will be analyzed	Primary endpoint: non-responder Key secondary endpoints: MI based on placebo group after ICE
Treatment discontinuation (not due to LoE, related AE nor lack of compliance)	Hypothetical	Depending on the subject's status until the last known visit and specific intercurrent event that contributed to the lost to follow-up, the relevant above intercurrent events will be considered for analyses.	Primary endpoint: MI based on randomized treatment Key secondary endpoints: MI based on randomized treatment
Stop of IMP but continues the study up to end of the Double-blind Treatment Period	Treatment-policy	The occurrence of missing IMP will be ignored, and data analyzed as planned to determine response status.	No action needed
Prohibited therapies	Composite / Hypothetical	Data after the intake of prohibited medication with a potential effect on the primary or key secondary endpoints will be disregarded.	Primary endpoint: non-responder Key secondary endpoints: MI based on placebo group after ICE
Concomitant therapies	Treatment policy	Data will be collected and analyzed regardless of whether an allowed concomitant therapy is given.	No action needed
Death not related to IMP or disease	Composite	Depending on the subject's status until the last known visit and specific intercurrent event that contributed to the lost to follow-up, the relevant above intercurrent events will be considered for analyses. No data beyond the date of death will be imputed.	Primary endpoint: MI based on placebo group Key secondary endpoints: MI based on placebo group

Intercurrent Event	Strategy	Description	Imputation details
Death related to IMP or disease	Composite	Death will be considered as treatment failure. No data beyond the date of death will be imputed.	Primary endpoint: non-responder Key secondary endpoints: imputing worst score / highest HR observed
Lost to follow-up	Hypothetical	Depending on the subject's status until the last known visit and specific intercurrent event that contributed to the lost to follow-up, the relevant above intercurrent events will be considered for analyses.	Primary endpoint: MI based on randomized treatment Key secondary endpoints: MI based on randomized treatment
Population-level Summary	Primary: Point estimate and 95% CI for the difference in proportions. Key secondary: Point estimate and 95% CI for difference in means.		

CI = confidence interval; ICE = intercurrent event; IMP = investigational medicinal product; LoE = lack of efficacy; MI = multiple imputation; POTS = Postural Orthostatic Tachycardia Syndrome

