## **7. SUBJECT WITHDRAWAL AND DISCONTINUATION OF INVESTIGATIONAL PRODUCT**

### **7.1. Discontinuation of Investigational Product**

Subjects may discontinue IMP at any time at their own request, or at the discretion of the investigator or the Sponsor for safety, behavioral, or administrative reasons.

Subjects who discontinue IMP will remain in the study to complete follow-up activities or allow data collection as detailed in the Schedule of Activities (Section 1.3).

If subjects discontinue IMP during the Double-blind Treatment Period, they are asked to complete the W25 treatment assessments at the study visit where IMP treatment is discontinued instead of the assessments scheduled for that particular visit. If subjects discontinue IMP during the Open-label Treatment Period, they are asked to complete the End of Treatment (EOT) assessments at the study visit where IMP treatment is discontinued instead of the assessments scheduled for that particular visit.

Subjects discontinuing IMP who decline further study procedures / visit participation will be withdrawn from the study (see Section 7.2).

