## 9. STATISTICAL CONSIDERATIONS

### 9.1. Statistical Hypotheses

The study is designed to test the null ( $H_{01}$ ) versus the alternative ( $H_{11}$ ) hypothesis of the primary endpoint for the proportion of subjects no longer meeting diagnostic criteria of post-COVID POTS as measured by standardized standing test (ie, no longer experiencing HR increase of  $\geq 30$  bpm, in the absence of orthostatic hypotension [ie, sustained 20 mmHg decrease of SBP]) at the end of the Double-blind Treatment Period.

$$H_{01}: P_{\text{IgPro20}} \leq P_{\text{Placebo}} \quad \text{versus}$$

$$H_{11}: P_{\text{IgPro20}} > P_{\text{Placebo}}$$

Where  $P_{\text{IgPro20}}$  and  $P_{\text{Placebo}}$  indicate the proportion of subjects no longer meeting diagnostic criteria of post-COVID POTS as measured by standardized standing test in the IgPro20 and placebo group, respectively. The test for superiority will be performed at a 1-sided alpha level of 2.5% using a Farrington-Manning test.

Hypothesis for the key secondary endpoints are:

$$H_{02}: \mu_{\text{IgPro20}} \geq \mu_{\text{Placebo}} \quad \text{versus}$$

$$H_{12}: \mu_{\text{IgPro20}} < \mu_{\text{Placebo}}$$

Where,  $\mu_{\text{IgPro20}}$  and  $\mu_{\text{Placebo}}$  correspond to the treatment group means of interindividual changes in OI score of COMPASS-31 for IgPro20 and placebo, respectively. The test for superiority will be performed using a  $t$ -test.

$$H_{03}: \mu_{\text{IgPro20}} \geq \mu_{\text{Placebo}} \quad \text{versus}$$

$$H_{13}: \mu_{\text{IgPro20}} < \mu_{\text{Placebo}}$$

Where  $\mu_{\text{IgPro20}}$  and  $\mu_{\text{Placebo}}$  correspond to the treatment group means of interindividual changes in COMPASS-31 total score for IgPro20 and placebo, respectively. The test for superiority will be performed using a  $t$ -test.

$$H_{04}: \mu_{\text{IgPro20}} \geq \mu_{\text{Placebo}} \quad \text{versus}$$

$$H_{14}: \mu_{\text{IgPro20}} < \mu_{\text{Placebo}}$$

Where  $\mu_{\text{IgPro20}}$  and  $\mu_{\text{Placebo}}$  correspond to the treatment group means of interindividual changes in HR for IgPro20 and placebo, respectively. The test for superiority will be performed using a  $t$ -test.

Testing will be performed accounting for multiplicity as outlined in Section 9.4.3 to preserve the alpha level of 2.5%.

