### 9.2. Sample Size Determination

Based on the rationale presented in Section 4.3, assuming the proportion of subjects no longer meeting diagnostic criteria of post-COVID POTS as measured by standardized standing test at the end of the Double-blind Treatment Period. Sample size assumptions are based on the 30% and 60% response for the placebo and IgPro20 group, respectively; under

these assumptions, at least 126 subjects will be required to provide 90% power (2:1 randomization) to detect a 30% difference in proportion of responders using a Farrington-Manning test for a 1-sided alpha of 2.5%. An additional 18 subjects will be randomized to account for a futility analysis at 54 subjects, and an additional 33 subjects will be randomized to ensure > 100 subjects treated with IgPro20 for >1 year will be achieved considering approximately 20% early drop out. Therefore, the final number of patients to be randomized is 177 (118:59).

For hypothesis testing, an alpha of 2.5% (1-sided) will be used. Randomization will be continued if the dropout rate is over 10%.

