#### 9.4.4. Multiple Imputation

For subjects with an ICE (see Section 9.4.2.1.1) that considers multiple imputation data after the ICE will be disregarded (if applicable) and be imputed using a multiple imputations approach.

**Intermittent missing replacement step:** If intermittent values are missing for any of the data included in the multiple imputation analysis, the intermittent values will be imputed first using a Markov Chain Monte Carlo method 50 times to create 50 data sets with only monotone missing. The corresponding data sets will be used as input data sets for replacement of the post-ICE missing values using monotone regression; as the preceding step led already to 50 data sets, the number of imputations in this step is to be set to 1.

**Imputation step:** Replacement of missing values for HRW5,0min, HRW5,10min, HRW9,0min, HRW9,10min, HRW13,0min, HRW13,10min, HRW17,0min, HRW17,10min, HRW21,0min, HRW21,10min, HRW25,0min, and HRW25,10min, OIW5, OIW9, and OIW25 as well as TSW5, TSW9, and TSW25 (if

applicable), will be done using multiple imputations based on monotone regression with the covariates treatment, country, HR at baseline, COMPASS-31 TS and OI at baseline and HR and COMPASS-31 TS and OI values from previous weeks by SAS® PROC MI for 50 imputations with a seed of 7562032. The HR value at the end of the standing test will be considered as the average of the two highest values within 10 minutes after start of the standing test.

**Analysis step:** For each of the 50 analyses of the primary and key secondary endpoints will be performed as outlined in Section 9.4.2.1 and Section 9.4.2.2.

For the primary endpoint, each subject's response status will be derived as in Section 9.4.2.1.

For the first key secondary endpoint, the imputed HR will be used.

For the second and third key secondary endpoints, the imputed COMPASS-31 values will be used.

**Combination step:** The corresponding results across the data sets are combined for overall inference using SAS® PROC MIANALYZE according to Rubin's rule to give the 1-sided p-values for hypothesis testing, and the corresponding measures (responder rate, mean, 95% CIs, as applicable).

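### Protocol Table 5 gives a subject who stops IMP but stays to Week 25 conflicting outcomes with no precedence, and the imputation in Section 9.4.4 does not implement the table

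*Protocol*

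**What the plan says.** Protocol Table 5 has three rows on stopping IMP, numbered here in table order.

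- **Row 1**, stopping for lack of efficacy, a related adverse event or non-compliance: non-responder on the primary endpoint, placebo-based multiple imputation (MI) on the key secondary endpoints. On data use: "Only data collected prior to treatment (IMP) discontinuation will be analyzed".
- **Row 2**, stopping for any other reason: MI based on the randomized arm.
- **Row 3**, stopping but continuing to the end of the double-blind period: treatment policy. "The occurrence of missing IMP will be ignored, and data analyzed as planned to determine response status".

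Section 7.1 sets the expected conduct: "Subjects who discontinue IMP will remain in the study to complete follow-up activities or allow data collection".

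The Table 5 row for death unrelated to IMP or disease states "No data beyond the date of death will be imputed", yet its imputation column prescribes placebo-based MI for the primary and key secondary endpoints.

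Section 9.4.2.1 requires two things of a responder at Week 25: a heart rate (HR) increase below 30 bpm and a systolic pressure (SBP) fall of less than 20 mmHg. Section 9.4.4 lists the variables to impute: HR at Weeks 5, 9, 13, 17, 21 and 25, and the COMPASS-31 orthostatic intolerance (OI) and total (TS) scores at Weeks 5, 9 and 25. It uses one monotone regression with treatment among the covariates, and then "For the primary endpoint, each subject's response status will be derived as in Section 9.4.2.1".

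**The concern.** Rows 1 and 2 are defined by why the subject stopped, and row 3 by what the subject did next. A subject who stops and stays meets both descriptions, and nothing says which wins. Two analysts following the protocol could give the same subject different outcomes. Because row 1 includes related adverse events, the share affected may differ by arm, so the choice could move the treatment difference as well as the two rates.

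Section 9.4.4 should turn Table 5 into data, but it leaves out a component of the responder rule, half of the COMPASS-31 visits, and the reference-arm model that several rows call for.

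**Working it through.** **1. The plan's own sample size.** Protocol Section 9.1 sets a Farrington-Manning test at one-sided 2.5%. Section 9.2 takes response rates of 30% (placebo) and 60% (IgPro20), and concludes "at least 126 subjects will be required to provide 90% power (2:1 randomization) to detect a 30% difference in proportion of responders".

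Pooled score test, allocation k = 2, p̄ = (0.30 + 2 × 0.60)/3 = 0.50:

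n(placebo) = [1.960 × √(1.5 × 0.25) + 1.2816 × √(0.21 + 0.24/2)]² / 0.30² = (1.200 + 0.736)² / 0.09 = 41.7, so 42.

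The total is 42 + 84 = 126, which reproduces the stated figure. Power is 90.2%. Adding 18 and 33 gives 177 (118:59), with power 97.3% at the planned rates.

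**2. One subject, two rows.** Take a subject who stops IMP at Week 13 and is assessed at Week 25.

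| Reason for stopping | Rule by reason | Rule by row 3 |
|---|---|---|
| Lack of efficacy, related AE, non-compliance | Non-responder; later data unused | Observed Week 25 response |
| Any other | MI from own arm | Observed Week 25 response |

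**3. Size of the row 1 / row 3 conflict (assumed inputs).** Let s be the share of an arm that stops for a row 1 reason and stays, and r their observed Week 25 response rate. Using row 1 in place of row 3 lowers that arm's rate by s × r. For IgPro20 with s = 10% and r = 50%: 0.10 × 118 ≈ 12 subjects, 6 of them responders, and 6/118 = 5.1 points.

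Setting r to the planned 60% and 30% gives the following (row 3 throughout: 30 points, power 90.2% at 126 and 97.3% at 177).

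| s | Row 1, both arms: difference; power at 126 / 177 | Row 1, IgPro20 only: difference; power at 126 / 177 |
|---|---|---|
| 5% | 28.5; 87.2% / 95.9% | 27; 83.0% / 93.5% |
| 10% | 27; 83.6% / 94.0% | 24; 73.3% / 86.9% |
| 20% | 24; 75.3% / 88.6% | 18; 48.7% / 63.4% |

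The direction is not fixed. If only placebo subjects were affected at s = 10%, the placebo rate would be 0.30 × 0.90 = 27% and the difference 33 points.

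**4. Imputation list against what is needed.** Double-blind post-baseline visits listed in Section 9.4.4:

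| Variable | Listed | Needed for |
|---|---|---|
| HR, supine and standing | 6 of 6 | Primary; HR key secondary |
| SBP | 0 of 6 | Primary |
| OI and TS | 3 of 6 (Weeks 13, 17, 21 absent, though scheduled) | OI and TS key secondaries |

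An imputed HR increase of 30 bpm or more is a non-response whatever the SBP. An imputed increase below 30 bpm has no derivable response. If a share m of an arm is imputed and a share h of those have an increase below 30 bpm, m × h of the arm is undefined. With assumed m = 10% and h = 60%, that is 6 points at most. The actual effect is m × h × q, where q is the share who would fail on SBP; the documents give no q.

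**5. Reference model.** Table 5 asks for placebo-based MI in row 1 and prohibited therapies (key secondary endpoints) and in unrelated death (all of these endpoints). With treatment as a covariate in a single regression, IgPro20 subjects are imputed with the IgPro20 effect. That suits the rows based on the randomized arm and not the placebo-based ones.

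**6. What SAP v2.0 changes.** Sections 5, 10.2.2, 10.3 and 10.6 drop MI after termination with 16 of 177 randomized, and Section 10.2.1 says the primary estimand cannot be assessed. Table 10 makes row 1 stoppers non-responders at all later visits and has no treatment-policy row. It covers response only. Section 10.3 summarizes the key secondary endpoints on available data without saying whether values after a row 1 or prohibited-therapy event count. Sections 5 and 10.2.1 also say only observed data are presented, while Table 10 assigns non-response at later visits regardless of what was observed.

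**The case against.** The strongest reply is that the operative plan has moved on. SAP v2.0 runs no MI, so the SBP, COMPASS-31, reference-model and death points affect no result that will now be produced, and Table 10 settles row 1 response. This stands, and it limits the point to the protocol's planned analysis. A reader might take SAP Table 1, which still cites Protocol Table 5 for intercurrent events, as proof that the conflict is live. It is not: Table 1 sits in SAP Section 4, which Section 3 says describes the initial design.

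A second reply is that rows 1 and 2 may mean subjects who leave the study. Row 2's description, which speaks of the last known visit and loss to follow-up, gives this some support. It does not work for row 1: excluding data after discontinuation presupposes that such data exist, Section 7.1 keeps stoppers in the study, and loss to follow-up has its own row.

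A third is that Section 7.1 moves the Week 25 assessments to the visit at which IMP is stopped, so true Week 25 data after stopping may be scarce. This reduces the likely number affected, by an amount the documents do not show.

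A fourth is that Protocol Section 9.4 calls itself a summary and SAP version 1.0 is not available; it may have specified SBP or a placebo-reference model. That is possible, but it would not remove the contradictions printed in Table 5.

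**Conclusion.** Wrong as written, in the protocol's planned analysis. The three discontinuation rows overlap without precedence, Section 9.4.4 does not implement Table 5, and the unrelated-death row contradicts itself. The row choice is worth about 5 points on the IgPro20 rate if 10% of that arm are row 1 stoppers who stay and half respond. These shares are assumptions, and the difference could move either way.

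Three stronger readings are not supported.

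- A reader might infer that the primary estimand cannot be computed at all. Response is defined for subjects with observed Week 25 data and no such event; the estimate loses uniqueness only through affected subjects. The COMPASS-31 gap is outside the responder rule. It mainly touches the OI and TS key secondaries, and since the covariates include values from previous weeks it is partly an ambiguity.
- A reader might infer that imputed subjects can never fail on SBP and so face an easier rule. Section 9.4.4 keeps the two-part rule and is silent on where SBP comes from; it does not waive it.
- A reader might infer that the current descriptive analysis is blocked. It is not; only the two SAP wording points in step 6 remain.

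**What to change.** **Protocol Table 5.** State an order of precedence among the three discontinuation rows. Row 1 over row 3 is consistent with SAP Table 10. State whether row 2 or row 3 governs other stoppers who have Week 25 data. This should follow the intended estimand: restricting row 2 to subjects without Week 25 data would replace a hypothetical strategy with treatment policy for the rest. Give unrelated death one consistent rule.

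**Protocol Section 9.4.4.** Add supine and minimum standing SBP at each visit (the quantities SAP Section 8.2.3 already uses) and OI and TS at Weeks 13, 17 and 21. Specify a placebo-reference model for the rows that call for it, and keep the treatment-covariate model for the others.

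**SAP v2.0, for the terminated dataset.** In Section 10.3, say whether key secondary values after a row 1 or prohibited-therapy event enter the by-visit summaries. In Sections 5 and 10.2.1, reconcile the observed-data statement with Table 10.

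The cost is wording and, if the protocol analysis is reused, imputation code. No new data are needed.

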#### 9.4.2.1.2. Sensitivity Analysis

The following sensitivity analyses are planned for the primary efficacy endpoint:

- Using the PP analysis set.
- Using a tipping point analysis: for subjects with an ICE (see Section 9.4.2.1.1 for further details), the HR after the ICE will be imputed using a multiple imputations approach (see Section 9.4.4 for further details).

#### 9.4.2.2. Analysis of Key Secondary Endpoints

To further evaluate the efficacy of IgPro20 in adult subjects with post-COVID POTS, the following key secondary endpoints will be conducted:

1. Change from baseline in OI score of COMPASS-31 at the end of Double-blind Treatment Period

For each subject  $OI_{\text{change}} = OI_{W25} - OI_{\text{baseline}}$  will be calculated, where  $OI_{W25}$  corresponds to the OI score of COMPASS-31 at Week 25 and baseline, respectively. Descriptive statistics of the individual changes will be calculated by treatment group, including means and 95% CIs. Treatment group means will be tested for superiority by using a *t*-test. Hypothesis testing as outlined in Section 9.1 will be done.

2. Change from baseline in TS of COMPASS-31 at the end of the Double-blind Treatment Period

For each subject  $TS_{\text{change}} = TS_{W25} - TS_{\text{baseline}}$  will be calculated, where  $TS_{W25}$  corresponds to the TS of COMPASS-31 at Week 25 and baseline, respectively. Descriptive statistics of the individual changes will be calculated by treatment group, including means and 95% CIs. Treatment group means will be tested for superiority by using a *t*-test. Hypothesis testing as outlined in Section 9.1 will be done.

3. Change from baseline in HR increase within 10 minutes of standing test at the end of the Double-blind Treatment Period:

For each subject  $HR_{\text{change}} = (HR_{W25,10\text{min}} - HR_{W25,0\text{min}}) - (HR_{\text{baseline},10\text{min}} - HR_{\text{baseline},0\text{min}})$  will be calculated, where  $HR_{W25,10\text{min}}$  indicates the average of the two highest HR measures (bpm) within 10 minutes after start of the standing test at W25,  $HR_{W25,0\text{min}}$  indicates the HR measure (bpm) at start of the standing test at Week 25, and likewise for baseline. Descriptive statistics of the individual changes will be calculated by treatment group, including means and 95% CIs. Treatment group means will be tested for superiority by using a *t*-test. Hypothesis testing as outlined in Section 9.1 will be done.

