#### 9.4.3. Multiplicity

Issues related to multiplicity arising from testing the primary endpoint and key secondary endpoints will be addressed using pre-defined hierarchical testing procedure of the primary and key secondary endpoints with following order at an alpha level of 2.5%:

1. Hypothesis tested: primary endpoint
2. Hypothesis tested: 1st key secondary endpoint; change from baseline in OI domain of the COMPASS-31
3. Hypothesis tested: 1st key secondary endpoint; change from baseline in COMPASS-31 total score
4. Hypothesis tested: 2nd key secondary endpoint; change from baseline in HR increase

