10.3.1. Analysis of Key Secondary Endpoints

The following key secondary efficacy endpoints are defined:

1. Change from baseline in OI score of COMPASS-31 at the end of the Double-blind Treatment Period

For each subject $OI_{\text{change}} = OI_{W25} - OI_{\text{baseline}}$ will be calculated, where OI_{W25} corresponds to the OI score of COMPASS-31 at Week 25 and baseline, respectively. Descriptive statistics of the individual changes will be calculated by treatment group.

2. Change from baseline in TS score of COMPASS-31 at the end of the Double-blind Treatment Period:

For each subject $TS_{\text{change}} = TS_{W25} - TS_{\text{baseline}}$ will be calculated, where $TS_{W25} / TS_{\text{baseline}}$ correspond to the TS score of COMPASS-31 at Week 25 and baseline, respectively. Descriptive statistics of the individual changes will be calculated by treatment group.

3. Change from baseline in HR increase within 10 minutes of standing test at the end of the Double-blind Treatment Period:

For each subject $HR_{\text{change}} = (HR_{W25,10\text{min}} - HR_{W25,0\text{min}}) - (HR_{\text{baseline},10\text{min}} - HR_{\text{baseline},0\text{min}})$ will be calculated, where $HR_{W25,10\text{min}}$ indicates the average of the two highest HR measures (bpm) within 10 minutes after start of the standing test at W25, $HR_{W25,0\text{min}}$ indicates the HR measure (bpm) at start of the standing test at Week 25, and likewise for baseline. Descriptive statistics of the individual changes will be calculated by treatment group.

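### The three key secondary changes are compared by a t-test without baseline as a covariate, which is valid but gives up precision of unknown size

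*Protocol*

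**What the plan says.** Protocol 9.4.2.2 computes, for each subject, Week 25 minus baseline for the OI score, the COMPASS-31 total score and the HR increase. The third endpoint reads "Change from baseline in HR increase within 10 minutes of standing test at the end of the Double-blind Treatment Period". The instruction is the same for all three: "Descriptive statistics of the individual changes will be calculated by treatment group, including means and 95% CIs", then "Treatment group means will be tested for superiority by using a" t-test. Protocol 9.1 repeats the t-test for each hypothesis. No covariate appears in either section, and the sensitivity analyses (per-protocol set, tipping point) add none.

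Baseline is used elsewhere. Protocol 9.4.4 includes baseline HR, COMPASS-31 total score and OI score as covariates when imputing missing values. Its analysis step then returns to the tests of 9.4.2.1 and 9.4.2.2.

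Protocol 9.4.3 places these endpoints second, third and fourth in a "pre-defined hierarchical testing procedure of the primary and key secondary endpoints with following order at an alpha level of 2.5"%. Protocol 9.2 powers the primary endpoint only.

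SAP 4.2.2 repeats the t-test, but SAP 3 says that SAP section 4 describes the design as initially planned. For the analysis now to be reported, SAP 10.3.1 says only "Descriptive statistics of the individual changes will be calculated by treatment group".

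**The concern.** A change score fixes the coefficient on baseline at exactly 1. When the true slope of the Week 25 value on baseline is below 1, subtracting the whole baseline leaves part of the baseline variation in the error term of the t-test. ANCOVA estimates that slope and removes this part.

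The covariates are measured, and the imputation model already names them. They are missing only from the step that produces the p-value. Three of the four hypotheses in the fixed sequence depend on this test, and a miss on the OI score would close off the total score and the HR increase. No power is stated for any of the three, so the plan shows no margin against which a loss of precision could be judged.

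**Working it through.** **1. The plan's own figure.** The only sample size statement is for the primary endpoint: "Sample size assumptions are based on the 30% and 60% response for the placebo and IgPro20 group, respectively", and "at least 126 subjects will be required to provide 90% power (2:1 randomization"). The test is described thus: "The test for superiority will be performed at a 1-sided alpha level of 2.5% using a Farrington-Manning test". At a null difference of zero the Farrington-Manning test uses the pooled variance. With 30% against 60%, 2:1 allocation and one-sided 2.5%, this gives 42 + 84 = 126 subjects and power of 90.2%. The stated 126 reproduces exactly. It does not bear on the key secondary endpoints.

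**2. Inputs for the key secondary endpoints.**
- Planned allocation: 118:59 (protocol 9.2).
- Level: one-sided 2.5% (protocol 9.1 and 9.4.3).
- SDs and baseline-to-Week-25 correlation (rho): not in the documents. Assumed: rho from 0.3 to 0.7, with three cases for the SDs.
- Starting power of 80% for the t-test: assumed, for illustration only.

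**3. Formulas.** Let s0 and s1 be the SDs at baseline and Week 25, and k = s1/s0. With a common slope in both arms, the variances of the treatment difference are:
- change score: (s0² + s1² − 2·rho·s0·s1) × (1/118 + 1/59)
- ANCOVA: s1²·(1 − rho²) × (1/118 + 1/59)

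The allocation term cancels, so the ratio of ANCOVA to change-score variance is (1 − rho²)k² / (k² + 1 − 2·rho·k). It is at most 1 in large samples and equals 1 only when rho·k = 1. With k = 1 it reduces to (1 + rho)/2. Power after adjustment is Φ((0.8416 + 1.96)/√ratio − 1.96).

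**4. Entry truncation.** COMPASS-31 baseline is the Screening value, which must be at least 40. The schedule has no standing test on Day 1, so baseline HR increase also comes from Screening, where at least 30 bpm is required (40 bpm at age 18 to 19). Suppose, as an assumption, that these limits remove the lower half of a normal baseline distribution. The baseline variance falls to 1 − 2/π = 0.363 of its original value, while the slope and residual variance are unchanged. The ratio becomes (1 + rho) / ((1 − rho)·0.363 + 1 + rho), where rho is the correlation before selection. At rho = 0.5 this is 1.5 / (0.182 + 1.5) = 0.89.

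**5. Results.**

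| Case | rho 0.3 | rho 0.5 | rho 0.7 |
|---|---|---|---|
| Variance ratio, equal SDs | 0.65 | 0.75 | 0.85 |
| 80% power becomes | 93.5% | 89.9% | 86.0% |
| Variance ratio, lower half cut off at entry | 0.84 | 0.89 | 0.94 |
| 80% power becomes | 86.5% | 84.3% | 82.4% |
| Variance ratio, Week 25 SD 1.5 times baseline SD | 0.87 | 0.96 | 1.00 |
| 80% power becomes | 85.1% | 81.4% | 80.1% |

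Simulation at 118:59 with equal SDs gave 0.65, 0.75 and 0.86. In that most favourable case, the t-test on 177 subjects is as precise as ANCOVA on 177 × 0.65 = 115 to 177 × 0.85 = 150, so about 27 to 62 subjects' worth of information is given up.

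**The case against.** The strongest reply is that the t-test is a legitimate pre-specified analysis. Randomization protects it, and the documents contain no SD, correlation, effect size or power target for these endpoints, so no stated property is missed. The gain could be close to nil. The trial has also ended: SAP sections 5, 10.3 and 10.5 drop imputation, testing and multiplicity, so an amended protocol test would change no reported result. All of this stands. It limits the point to the efficiency of the protocol's planned analysis.

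Four stronger readings are tempting but not supported:

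- *Baseline is discarded.* It is subtracted in every endpoint and enters the imputation model. Only the covariate in the analysis model is missing.
- *The comparison is biased or the error rate inflated.* Chance baseline imbalance and regression to the mean affect randomized arms alike in expectation. They add variance, not bias.
- *The entry thresholds make the loss larger.* Truncation lowers the correlation, but it also shrinks the baseline SD, so the equal-SD formula no longer applies. The second case in the table shows that the gain from ANCOVA falls.
- *The reduced report on 16 subjects is dominated by baseline imbalance.* SAP 10.3 and 10.3.1 plan statistics within each arm and specify no between-arm difference. Even if a reader took one, with an assumed 11:5 split the SE of the baseline difference is √(1/11 + 1/5) = 0.54 SD. At rho 0.5 and equal SDs a typical imbalance contributes 0.5 × 0.54 = 0.27 SD. The SE of the raw change difference is √(2 × 0.5) × 0.54 = 0.54 SD. Imbalance is therefore (0.27/0.54)² = 25% of the variance; the rest is small-sample noise that adjustment does not remove.

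**Conclusion.** The point holds as a loss of precision in the protocol's planned key secondary analysis. Over rho 0.3 to 0.7, adjustment would cut variance by 15% to 35% with equal SDs, by about 6% to 16% if entry removes the lower half of baseline values, and by 0% to 13% if the Week 25 SD is 1.5 times the baseline SD. The 15% to 35% range should not be quoted without the equal-SD condition. The truncation case applies most directly to the total score and the HR increase, because OI is selected only through the total score.

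The ranges rest on assumed correlations, SD ratios and truncation, a common baseline slope in both arms, and an 80% starting power that the documents do not state. Because the three tests run in sequence, lost power on an earlier one also limits the later ones, but the documents do not allow that effect to be sized. Validity is not in question, and nothing in the analysis that SAP 2.0 will report is affected.

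**What to change.** In protocol 9.4.2.2 and 9.1, replace the t-test for each key secondary endpoint by ANCOVA of the Week 25 change on treatment, with that endpoint's own baseline as covariate. Fit it in each of the 50 imputed data sets and combine the treatment estimates by Rubin's rule, as protocol 9.4.4 already does for the present analysis. Keep the one-sided 2.5% level and the testing order of 9.4.3.

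The cost is revised wording and one model statement per endpoint, with no new data or visits. SAP 4.2.2 should stay as it is, because it records the initial design, and SAP 10.3.1 needs no adjusted comparison. Since the trial was terminated, the practical value of the change lies in any reuse of this design.
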